4.3 Triathlon PKR Partial Knee Resurfacing System

4.3.1 Femoral Component

The Triathlon PKR femoral component is fabricated from cast-cobalt-chromium- molybdenum alloy and has two fixation pegs. The system is intended for cemented fixation. The bone/cement facing surface of the component is grit blasted and the articulating surface is highly polished.

The Triathlon PKR femoral component was designed with the same philosophy and rational at the Triathlon Total Knee System to have a Single Radius to recreate the natural movement of the epicondyle (in 10°-110° range). Triathlon PKR Partial Knee Resurfacing System incorporates a simple two-step gap balancing system to help balance the flexion and extension gaps so the femoral component is positioned well and normal physiologic ligament tension may be restored.

It is available in 6 sizes ranging from Size 1 to Size 6 in right lateral/left medial and left lateral/right medial configurations.

4.3.2 Tibia Baseplate

The Triathlon PKR tibia baseplate is fabricated from cast-cobalt-chromium-molybdenum alloy. The system is intended for cemented fixation.

The underside of the tibial component contains a cement recess, a round peg and an angled peg for cement fixation and to provide stability. The inside of the tray has tabs and lip for locking the tibial insert in place. The surface finish of the underside of the baseplate is grit blasted and the topside is bead blasted.

It is available in 6 sizes ranging from Size 1 to Size 6 in right lateral/left medial and left lateral/right medial configurations.

4.3.3 Insert

The Triathlon PKR inserts are manufactured from ultra high molecular weight polyethylene (ASTM F648). Highly crosslinked (sequentially linked) X3™ polyethylene inserts.

The articular surface of the Triathlon PKR insert is designed to allow the following kinematics: Range of Motion 0° hyperextension to 135° flexion.

The Triathlon PKR insert is available in six sizes with thicknesses of 8mm, 9mm, 10mm and 12mm for the right lateral/left medial and left lateral/right medial compartments.

5 SELECTION OF PATIENTS

5.1 Participating Institutions

Up to sixteen institutions willing to participate in the Stryker Registry need to recruit at least 20 patients and maximum 100 patients. Institutions must fulfil the local and international applicable regulatory requirements. Sufficient human and technical resources in the centre are expected to ensure optimal data collection. Site selection will be performed according to Stryker Clinical procedures.

5.2 Number of patients

Up to 1600 patients who will receive a Total Knee Arthroplasty (TKA) replacement surgery involving either:

- Scorpio NRG Total Knee System with X3 insert
- Triathlon Total Knee System with X3 insert

or Partial Knee Resurfacing (unicompartmental knee arthroplasty, UKA) involving:

Triathlon PKR (Partial Knee Resurfacing) System with X3 insert

will be enrolled in the register. Patients will be enrolled prospectively.

5.3 Patient selection criteria

All patients in a participating centre matching all of the inclusion criteria (no specific exclusion criteria) and who receive either the (TKA) surgery involving the Scorpio NRG or Triathlon Total Knee System with X3 inlay or a partial knee resurfacing (unicompartmental knee) involving the Triathlon PKR (Partial Knee Resurfacing) System will be recorded in the Stryker Registry.

5.3.1 Inclusion criteria

Patients suitable for inclusion in the outcomes registry will be those fulfilling all the following selection criteria:

- Patients requiring primary TKA, suitable for the use of the Scorpio NRG with X3 insert or Triathlon Total Knee System with X3 insert, or, patients requiring partial knee resurfacing (unicompartmental knee) suitable for the use of the Triathlon PKR (Partial Knee Resurfacing) System with X3 insert
- 2. Patients who understand the conditions of the outcomes registry and are willing and able to comply with the standard post-operative evaluations and the prescribed rehabilitation.

3. Patients who signed the Informed Consent Form (approved by Ethics Committee if required) prior to surgery.

The patient will be informed by the Investigator (or his designated representative) of the purpose of the data collection. The patient will be informed that his/her medical records are subjected to review as necessary. The confidentiality of the patient will be maintained at all times and the collected data will be anonymous. The patient will be told that he/she is free to refuse the collection of his/her clinical data and to withdraw from the Surveillance at any time without compromising future medical care. A signed Patient Informed Consent will be obtained prior to patient participation (APPENDIX II - PATIENT INFORMATION SHEET AND INFORMED CONSENT).

5.3.2 Exclusion criteria

There are no exclusion criteria for the NTX Registry

5.4 Patient ID

Each patient participating in the registry will be allocated a unique number for the duration of the surveillance. The investigator will maintain a personal subject identification list (subject numbers with the corresponding subject names) to enable records to be identified.

6 STUDY DURATION

It is anticipated that the patients shall be recruited within a 12 month period at each participating centre. The length of surveillance and patient visit schedule is based on the routine procedures of the institution. The surveillance system is set-up to record data at preoperative, intra-operative and 1 year, 3 years, 5 years, 7 years and 10 years follow-up.

Visit schedule

VISIT	TIME WINDOW
Pre-op.	Date of or any time post the date of written informed
Operation	N/A
1 year post-op.	± 3 months
3 years post-op.	± 6 months
5 years post-op.	± 6 months
7 year post-op	± 6 months
10 years post-op.	± 6 months

6.1 Patient Evaluations

Patients will be assessed pre-operatively, per-operatively and post-operatively. The follow-up intervals will be the normal routine of the institutions.

6.1.1 Pre-operative Evaluation

- Clinical History

- Patient ID (Register, Site, Subject) e.g. TRI-01-001
- · Date of birth, weight, height, Gender
- Visit Date
- Cigarette and Alcohol use
- Previous surgery to knee planned for operation
- Primary diagnosis
- Pain medication (in last 48 hours)

- Clinical Evaluation

- Patient ID (Register, Site, Subject)
- Operative side
- Date of informed consent signed
- Inclusion / Exclusion criteria
- KSS (Knee Society Score)
- Knee Injury and Osteoarthritis Outcome Score (KOOS) and EQ5D

6.1.2 Intra-operative Evaluation

- Surgical details

- Patient ID (Register, Site, Subject)
- Surgery Date
- Operative Side
- Surgical approach
- Navigation used
- Soft tissue release
- Type of Anesthesia
- Duration of surgery
- Intra-operative adverse events
- Components used and sizes
- Systemic antibiotic prophylaxis

6.1.3 Post-operative Evaluation

Patients will be assessed post operatively as the schedule for follow-up routine of the participating centre.

- Clinical Evaluation

- Patient ID (Register, Site, Subject)
- Date of assessment
- Adverse events
- Pain medication (in last 48 hours)
- KSS
- KOOS and EQ5D

6.1.4 Adverse events and device removal events

- Patient ID (Register, Site, Subject)
- Onset date
- When Did the event occur (Intra-op, Post-op)
- Operative site events
- Systemic events
- Device/procedure related
- Seriousness
- Treatment
 - Revision/Removal of the entire system or system components
 - Reoperations without component exchange
 - Other treatment
- Resolution of event

6.1.5 Termination

- Date of termination of Surveillance
- Reason for termination

7 ADVERSE EVENTS

The investigator is required to document all operative site and general medical adverse events as well as elective surgery involving other joints over the course of the 10 year surveillance period. Data to be collected includes date of occurrence, date diagnosed, type of complication and treatment.

7.1 Definitions

The following definitions are according to ISO 14155 from 2011.

7.1.1 Adverse event (AE)

"Any untoward medical occurrence, unintended disease or injury, or untoward clinical signs (including abnormal laboratory findings) in subjects, users or other parties, whether or not related to the investigational medical device

NOTE: This definition includes events related to the procedures involved."

Surgical procedures themselves are not adverse events; they are therapeutic measures for conditions that require surgery. The condition for which the surgery is required is an adverse event, if it occurs or is detected during the Register follow-up period.

7.1.2 Serious adverse event (SAE)

"Adverse event that

- a) led to death,
- b) led to serious deterioration in the health of the subject, resulting in
- 1) a life-threatening illness or injury, or
- 2) a permanent impairment of a body structure or a body function, or
- 3) in-patient or prolonged hospitalization, or
- 4) medical or surgical intervention to prevent life-threatening illness or injury or permanent impairment to a body structure or a body function,
- c) led to foetal distress, foetal death or a congenital abnormality or birth defect

NOTE: Planned hospitalization for a pre-existing condition, or a procedure required by the protocol, without serious deterioration in health, is not considered a serious adverse event."

7.1.3 Adverse device effect (ADE)

"Adverse event related to the use of an investigational medical device

NOTE 1 This definition includes adverse events resulting from insufficient or inadequate instructions for use, deployment, implantation, installation, or operation, or any malfunction of the investigational medical device.

NOTE 2 This definition includes any event resulting from an error useor from intentional misuse of the investigational medical device."

7.1.4 Serious adverse device effect (SADE)

Adverse device effect that has resulted in any of the consequences characteristic of a serious adverse event

7.1.5 Unanticipated serious adverse device effect (USADE)

"Serious adverse device effect which by its nature, incidence, severity or outcome has not been identified in the current version of the risk analysis report

NOTE Anticipated serious adverse device effect (ASADE) is an effect which by its nature, incidence, severity or outcome has been identified in the risk analysis report."

7.2 Documentation and reporting of adverse event by the investigator

All subjects who have adverse events, whether considered associated with the use of the implant or not, must be monitored to determine the outcome.

The following causal relationships will be assessed:

- i) Event related to specific study device?
- ii) Event related to surgery procedure?

This will be reported by the surgeon as:

- Yes*
- No
- Uncertain*

*If Yes or Uncertain, the Adverse Event form shall be sent to Stryker within 24 hours.

All serious adverse events, serious adverse device effects, adverse device effects and unexpected adverse events, in accordance with the above definitions, must be reported to the sponsor within 24 hours from their occurrence, using the *Stryker Clinical Adverse Event Report Form* (according to Stryker Clinical procedures). Subsequent follow-up reports will be provided to the sponsor.

A *Stryker Clinical Adverse Event Report Form* should be completed by the investigator and sent by email or fax within 24 hours to the sponsor either:

- local clinical contact by email or fax or
- Clinical Study Manager_

[contact] [contact]

If at the time of sending the report, all details are not available by the investigator; the partially completed form must be sent with the available data and then the investigator will seek to obtain complementary information. The complementary information will be sent by the investigator to the sponsor as soon as it will be available.

In addition, all adverse events, serious or not, occurring between two planned visits will be reported in the CRF. Death will be both reported in the adverse event CRF and in the termination CRF pages.

Moreover the investigator should send to the Sponsor a copy of the imaging exam when performed at the time of the adverse event, as part of the standard post-marketing vigilance system for the CE certified Stryker products. The investigator will evaluate the adverse event and determine the most appropriate actions.

The sponsor will report adverse events to Competent Authorities and Ethic Committees that occur in accordance with applicable regulations.

stryker

[figure not shown]

Figure: Adverse Events Categorization chart (from ISO 14155:2011)

8 PATIENT WITHDRAWALS

Patients are free to withdraw from the Surveillance at any time and are under no obligation to provide a reason for doing so. Patients who withdraw from the Surveillance should have the reason for their withdrawal recorded on the termination case report forms (CRF's), if at all possible. All attempts should be made to ascertain whether any patient apparently lost to follow up has actually chosen not to return or is deceased.

9 ELECTRONIC DATA CAPTURE: eCRF

All the above-mentioned pre-operative patient assessments, intra-operative details and post-operative follow-up assessments will be recorded on a CRF (Case Report Forms) which will be provided to any centre being part of the NTX Registry.

The CRF will be provided electronically (secured electronic data capture: EDC). A patient blank paper case report form can be printed by surgeons wishing data collection on paper before data entry in the EDC. After EDC data entry, a hard copy can be printed as well for

each patient by the surgeon(s). The EDC system complies with the FDA and international requirements for electronic database(s) security and performances.

The system will be secured to prevent unauthorized access to the data or to the system by using the combination of user ID and password which will be provided by Stryker SA to the authorised users of each centre. The investigator will maintain a list of individuals who are authorized to enter or correct data in the system.

The surgeon and his/her other defined users will receive system documentation, training and support for the use of the EDC. All required information collected during the following period must be entered by the investigator or designated representative in the EDC. All data entry, modification or deletion will be recorded automatically in an electronic audit trail (tracking of the data entered or modified). The combination of both user ID and password will correspond to the surgeon electronic signature which will be required for patient data validation.

The secured database will be physically hosted by Stryker Orthopaedics Mahwah, New Jersey (US).

The upmost best will be done to maintain confidentiality and anonymity at all times by use of the unique registry patient ID code. Only this patient ID code (no patient names, addresses, hospital numbers) will be recorded in the database.

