The main difference between the Triathlon Total Knee system and the Scorpio NRG Total Knee system is beside the use of a single A/P radius also the use of a single M/L radius design for the Scorpio NRG realizing a large contact area and higher rotational freedom in the two orthogonal planes.

The Single Radius and Soft Tissue guided motion philosophy, coupled with the latest generation highly cross-linked polyethylene (X3) as the material for the articulating surface has the potential to offer patients a longterm solution to their knee disability. X3 polyethylene preserves the mechanical strength, resists oxidation and shows extremely low wear rates.

Summary

The higher demands placed on current and new implants by the younger typically more active patient population emphasizes the importance for prostheses that show consistent long-term results. As the Stryker Knee systems are evolutionary in design and based on proven concepts and prior implant strategies, it is anticipated that they will demonstrate efficacy and safety in the long-term, however as for all new technology or design, a close overview of the long term performance and outcome is essential to prove this.

The aim of this Stryker Clinical Registry is to determine the Scorpio NRG, Triathlon and X3 component survivorship over years within a large European multicentre user group.

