3 OBJECTIVES & METHODS

The objective of this registry is to provide outcomes information with regard to surgical and implant performance and patient clinical outcomes of the patients who are eligible for a either a Total Knee Arthroplasty (TKA) replacement surgery involving the Scorpio NRG or Triathlon Total Knee System or Triathlon PKR Partial Knee Resurfacing (unicompartmental knee arthroplasty, UKA), all of which with X3 inlay.

The register will follow the standard clinical procedures used by the institutions for patient selection for knee arthroplasty surgery, patient surgery and patient follow-up. Therefore there will be, with regard to this register, no additional assessment, examination, procedure or follow-up visits compared to those usually performed in the institution (routine standard normal procedures).

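### Tracing of lost patients (Section 8) asks about refusal and death but not about the implant, so a revision done elsewhere can be missed in the survivorship estimate

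*Combined protocol and SAP*

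**What the plan says.** The introduction states the purpose: "The aim of this Stryker Clinical Registry is to determine the Scorpio NRG, Triathlon and X3 component survivorship over years". Section 11.1 estimates survivorship by Kaplan-Meier, for revision of the whole system or of components and for re-operation without exchange. The synopsis (Study Duration) follows the implant for ten years unless revision, death, emigration or withdrawal comes first, and counts revision of any one part as a revision. A missed visit is not among the listed ends.

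For a patient who seems lost, Section 8 says: "All attempts should be made to ascertain whether any patient apparently lost to follow up has actually chosen not to return or is deceased". Section 6.1.5 lists two termination items, a date and "Reason for termination".

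Other provisions bear on revisions:
- Section 6.1.4 lists "Revision/Removal of the entire system or system components" among the treatments of an adverse event.
- Section 7 requires operative-site and general medical events to be documented over the ten years. Section 7.2 adds events between visits and says: "All subjects who have adverse events, whether considered associated with the use of the implant or not, must be monitored to determine the outcome".
- Section 5.3.1 allows record review: "The patient will be informed that his/her medical records are subjected to review as necessary". Section 10 gives monitors access to source records.
- Section 3 promises "no additional assessment, examination, procedure or follow-up visits compared to those usually performed in the institution".

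**The concern.** The synopsis intends the implant to be followed, but the one instruction for patients who stop attending asks about the patient only. A site can carry out Section 8 to the letter, learn that the patient is alive and chose not to come back, enter a date and a reason, and close the case without learning whether the knee has been revised.

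A patient dissatisfied with the result may seek revision at another hospital and stop attending the first. If that happens often enough, the patients who leave are those with the higher revision hazard, and Kaplan-Meier, which treats them as exchangeable with those still attending, reports survivorship that is too high. Enrolling more patients narrows the interval but leaves this bias in place. Implant status that nobody asked for at the time of loss is hard to rebuild at analysis: under Section 9 the central database holds only the patient code, and under Section 5.4 the identities stay on the site's list.

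**Working it through.** **1. What each provision reaches**

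| Provision | Reaches a revision elsewhere in a patient who no longer attends? |
|---|---|
| Synopsis, Study Duration | Sets the duty to follow the implant; gives no step for a lost patient |
| 6.1.4, 7, 7.2 (recording and reporting) | Only once the site knows of the event |
| 7.2 (outcome monitoring) | Only patients with an event already known |
| 5.3.1, 10 (record review, monitor access) | Do not say they extend to another hospital's records |
| 6.1.5 (termination reason) | Only if the patient volunteers it |
| 8 (tracing) | Contact is called for; implant status is not asked |

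**2. The plan's own figures.** The only sample-size figures are the cap and the per-centre limits: 16 × 100 = 1600, which matches the stated cap, and 16 × 20 = 320 if all sixteen centres recruit the minimum. The documents give no revision, death or loss rate, so every rate below is an assumption.

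**3. Size of the bias.** Assume a constant revision hazard, a curve showing 5.00% revised at 10 years, a share L = 20% lost at uniform times, and a hazard multiplied by k after loss. Then H = −ln(0.95) = 0.05129, and

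true risk = 1 − [(1 − L)·e^(−H) + L·∫₀¹ e^(−H(u + k(1 − u))) du].

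The integral is 0.9623, 0.9500, 0.9260 and 0.9029 for k = 0.5, 1, 2 and 3. For k = 2: 1 − (0.8 × 0.95 + 0.2 × 0.9260) = 5.48%.

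| k | True risk | Understatement (points) | In SE, N = 1600 | In SE, N = 320 |
|---|---|---|---|---|
| 0.5 | 4.75% | −0.25 | −0.4 | −0.2 |
| 1 | 5.00% | 0 | 0 | 0 |
| 2 | 5.48% | 0.48 | 0.8 | 0.3 |
| 3 | 5.94% | 0.94 | 1.5 | 0.7 |

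With 10% lost the true risk is 5.24% (k = 2) and 5.47% (k = 3); with 30% lost it is 5.72% and 6.41%.

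**4. Standard error.** SE = S·√(∫₀¹⁰ h / (N·Y(t)) dt), with S = 0.95, h = H/10, Y(t) = e^(−(h+d)t)·(1 − L·t/10) and d = −ln(0.70)/10 for 30% deaths. The integral of h/Y is 0.0712. So SE = 0.95 × √(0.0712/1600) = 0.63 points, and 0.95 × √(0.0712/320) = 1.42 points. In this model the death rate affects the SE only, not the bias.

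**5. A different loss model.** With exponential loss (20% by year 10) and true survivorship fixed at 95.0%, Kaplan-Meier shows 95.0%, 95.5% and 95.8% for k = 1, 2 and 3. Simulation at 1600 patients gave 95.0% for k = 1 and 95.8% for k = 3. The two models agree in direction and rough size.

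**6. What one trace recovers.** Let the 20% lost be split evenly over last visits at years 1, 3, 5 and 7, with a share p traced once at the next scheduled visit and then censored. Loss now comes earlier on average (year 4, not year 5), so the true risks are higher than in step 3. The gap is the true risk minus the Kaplan-Meier risk.

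| k | True risk | Gap, p = 0 | p = 0.5 | p = 1 |
|---|---|---|---|---|
| 2 | 5.57% | 0.57 | 0.45 | 0.34 |
| 3 | 6.13% | 1.13 | 0.89 | 0.66 |

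If instead the revision is itself the reason for not returning, in a share q = 20% of revised patients, the reported risk is 1 − e^(−(1 − q(1 − p))H). A true 5.00% then appears as 4.02%, 4.51% and 5.00% for p = 0, 0.5 and 1.

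**The case against.** The best defence is that the duty already exists. The synopsis follows the implant and does not end that follow-up at a missed visit; Section 7 is not limited to events treated at the index hospital; and a site that traces a patient and hears of a revision must record it. On this reading Section 8 merely sorts out deaths and refusals, and only its wording is thin. Much of this stands. A reader might infer that the plan abandons the implant once a patient is lost, and the synopsis does not support that. What remains is that the recording duties start with knowledge of the event, and no available step prompts a site to seek it.

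A reader might also take Section 3 as a bar on contacting such patients. It rules out extra assessments, examinations, procedures and visits; it does not mention contact, and Section 8 itself calls for tracing.

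Two further objections stand as limits. The consent form (Appendix II) and the CRF were not available to this review. Either could permit contact with other hospitals or hold an implant-status item, and nothing is inferred from their absence. And the size rests wholly on assumed rates. The register is descriptive and has no threshold that a half-point shift would cross.

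**Conclusion.** The point holds in a limited form. Section 8 falls short of the implant-level follow-up set out in the synopsis, and a revision done elsewhere in a non-attending patient can be missed. Survivorship is overstated if lost patients have a higher revision hazard. It is unbiased if loss is unrelated to revision, and slightly understated if their hazard is lower. The documents do not support the stronger inference that the reported curve will be too favourable.

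Under the stated assumptions (20% lost, 30% deaths, 5% shown as revised), the understatement of revision risk is about 0.5 points at hazard ratio 2 and 0.9 points at ratio 3. Of these, only ratio 3 at the full 1600 exceeds one standard error; at 320 patients both are below one. This is worth correcting because the repair is cheap and survivorship is the register's stated aim, not because a large bias has been shown.

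The lack of a stated censoring date in Section 11.1 might be read as a second error. It is not one: the glossary treats losses as censored, and Section 6.1.3 already records "Date of assessment".

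**What to change.** Bring Section 8 into line with the synopsis by adding a third item to the tracing sentence, after refusal and death: *or has had the index implant revised or re-operated elsewhere*. Limit this to what the patient's consent allows, and do not apply it to patients who have withdrawn consent. First check whether Appendix II and the CRF already provide for it.

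At termination, record the implant status, the date that status was ascertained and, if revised, the date of revision. Enter any revision found on the existing adverse-event form, with component and reason if obtainable; the patient may not know them.

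The cost is one more question in tracing that is already required and three termination items, with no added visit or examination. The downside is slightly more site work and possibly slightly less favourable survivorship. One trace sees revisions only up to its own date: with everyone traced at hazard ratio 2, the gap falls from 0.57 to 0.34 points and does not close. Patients who cannot be traced are not reached.

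Optionally, for clarity only, Section 11.1 could say that implants are censored at the date their status was last known, which for untraced patients is the last recorded assessment.
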